10.13 Deviation Handling

A study deviation is defined as an event within a study that did not occur according to the CIP or the Clinical Trial Agreement (CTA).

Planned deviations to the CIP will not be permitted. The investigator is not allowed to deviate from the CIP except under emergency circumstances to protect human subjects' rights, safety, and well-being or in unforeseen circumstances beyond the investigator's control. The investigator(s) must notify Medtronic and the reviewing IRB/EC of any deviation from the CIP when specific to the protection of the life or physical well-being of a subject in an emergency per local IRB/EC regulations.

All study deviations must be reported on the eCRF regardless of whether they were medically justifiable, inadvertent, or occurred to protect the subject in an emergency. Multiple deviations of the same type at the same visit (i.e., multiple, but not all, study assessment missed or completed outside of window) may be reported on one case report form. If the deviation involves a failure to obtain a subject's consent or is made to protect the life or physical well-being of a subject in an emergency, the deviation must be reported to the IRB/EC as well as Medtronic within five (5) working days. Reporting of all other study deviations should comply with IRB or EC policies, local laws, and/or Regulatory Authority requirements. Upon the study site becoming aware of the deviation, these must be reported to Medtronic as soon as possible. Refer to Table 9: Investigator Reports for deviation reporting requirements and timeframes.

Medtronic is responsible for analyzing deviations, assessing their significance, and identifying any additional corrective or preventive actions (e.g., amend the CIP, conduct additional training, terminate the investigation). Severe or repetitive investigator compliance issues may result in initiating a corrective action plan with the investigator and study site. In some cases, it may necessitate suspending enrollment until the problem is resolved or ultimately terminating the investigator's participation in the study. Medtronic will provide study site-specific reports to investigators, periodically summarizing information on deviations that occur at the study site.

Examples of study deviations include but are not limited to:

- Failure to obtain proper IC or failure to document IC process
- Failure to collect required study data (e.g., required questionnaires)

AFFIX (MaxTack ¹ Clinical Investiga				
MDT23014	Revision	3.0	Page 45 of 97	Medtronic

- Late reported adverse event
- Missed study visit
- Study visits occurring outside of the visit window
- Valsalva maneuver not done for physical examination
- Subjects for which informed consent is not collected
- Inclusion/exclusion criteria not met
- Subjects who become pregnant during study follow-up, as pregnancy may impact performance outcome measurements
- Missing hernia recurrence assessment at each time point for performance outcome measurements

If a subject becomes unexpectedly pregnant during the study, they will remain in the study, and pregnancy status will be assessed during follow-up visits. Pregnancies during the study will be considered protocol deviations.

10.14 Subject Exit, Withdrawal or Discontinuation

10.14.1 Preoperative Screen Failure

Subjects who provide study consent but are determined to be ineligible prior to the procedure due to preoperative inclusion or exclusion criteria will be considered a "preoperative screen failure" and will not require additional study follow-up visits. The reason for the screening failure will be clearly recorded on the applicable eCRFs, and subjects who are considered a preoperative screen failure will not count towards enrollment. Subjects who screen fail prior to surgery will not have AEs reported (Table : Subject Status Adverse Event Reporting). For preoperative screen failures, a limited amount of data must be recorded in the study database (e.g., consent date, reason(s) for not meeting eligibility, etc.).

10.14.2 Intraoperative Screen Failure

Subjects who provide study consent, experience the skin incision but then are determined to be ineligible during the procedure due to intraoperative exclusion criteria will be considered an "intraoperative screen failure" and will not require additional follow-up visits. For intraoperative screen failures, a limited amount of data will need to be recorded on any applicable eCRFs (e.g., consent information, reason(s) for not meeting eligibility etc.). Subjects who are considered screen failed during surgery will not have AEs and DDs reported.

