9.3 Exclusion Criteria

Subjects will be excluded from the study if they meet any of the following criteria:

Preoperative Exclusion Criteria:

- 1. Subject is undergoing an emergency surgery (e.g., lifesaving procedures performed where subject is in imminent danger of death, strangulated hernia, etc.)
- 2. Subject has history of 3 or more hernia repair procedures
- 3. Subject has existing mesh in the space where the physician needs to apply the new mesh to be fixated with the MaxTack[™] Motorized Fixation Device
- 4. Subject is scheduled (or anticipated to be scheduled) for additional surgery, and subsequent surgery would jeopardize previous application of study treatment
- 5. Subject has history of allergic reactions to Poly (Glycolide-co-L-IActide) (PGLA)
- 6. Subject has history of allergic reactions to the components of the intended mesh
- 7. Subject has any systemic or local ongoing infection at the time of the surgery
- 8. Subject has a Body Mass Index (BMI) greater than 45 kg/m²
- 9. Subject has life expectancy in the opinion of the investigator, of less than 3 years at the time of enrollment
- 10. Subject is pregnant (as determined by standard site practices) or is planning to become pregnant during study duration period.
- 11. Subject has participated or will participate in an investigational drug or device research study that would interfere with the results of this study
- 12. Subject's participation in the study may jeopardize the safety or welfare of the subject, as determined by the investigator
- 13. Subject is already enrolled or was previously enrolled in this study

Intraoperative Exclusion Criteria:

1. Subject did not receive the MaxTack[™] Motorized Fixation Device tacks to fixate the mesh

AFFIX (MaxTac Clinical Investi				
MDT23014	Revision	3.0	Page 35 of 97	Medtronic

- 2. Subject did not receive a Medtronic (including Covidien) mesh
- 3. Inability to comply with the mesh IFU
- 4. Subject required more than a single piece of mesh
- 5. Subject has a surgical wound classified as Class II (clean-contaminated), Class III (contaminated) or Class IV (dirty/infected) as defined by the CDC classification
- 6. Subject with an American Society of Anesthesiologists (ASA) score of Class 4, 5, or 6
- 7. Inability to close the hernia defect
- 8. Subject's procedure required a multi-stage repair
- 9. Subject's minimally invasive procedure required to convert to open

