9.4 Subject Enrollment

Prior to enrollment, patients should be fully informed of the details of study participation as required by applicable regulations, the site's respective IRB/EC, and Medtronic. Informed consent must be obtained from each subject before conducting any study-specific non-standard of care, using the informed consent form (ICF) approved by the IRB/EC and Medtronic.

There are two analyses set as described in Section 14: the Full Analysis Set (FAS) and Per Protocol Analysis Set (PPAS). The table below defines the enrollment types that may occur in the study and where these subjects may be analyzed.

Enrollment Type	Definition	Analysis Set
Preoperative	Subjects who have signed consent but do not meet eligibility	None
Screen Failure	criteria prior to the procedure (skin incision).	
Intraoperative	Subjects determined to be eligible prior to procedure, but who	None
Screen Failure	met any intraoperative exclusion criteria.	
Enrolled	A subject is considered enrolled in the study when:	FAS, PPAS
	• it is confirmed that the ICF is properly signed and dated,	
	• they meet all preoperative inclusion criteria,	
	• they meet no preoperative exclusion criteria,	
	• they meet no intraoperative exclusion criteria, and	
	 MaxTack[™] tacks are utilized for fixation 	

Table 2: Enrollment Type and Definitions

Refer to Figure 5 for an enrollment flowchart.

AFFIX (MaxTac Clinical Investi				
MDT23014	Revision	3.0	Page 36 of 97	Medtronic

10. Study Procedures

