 - Tack, mesh, and other fixation data
- Obtain surgeon satisfaction questionnaire
- Assess and report adverse events, device deficiencies, and study deviations, if applicable

As mentioned, if a subject no longer meets eligibility criteria during the procedure, the patient will be considered an intraoperative screen failure, and no AEs will be reported. For enrolled patients, adverse event and device deficiency collection begins at the time the skin incision is made. Only the specific medications need to be reported, and only for those specific medications that were taken within 30 days of the procedure.

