11.4 Risk-Benefit Rationale

As described in the IFU for the MaxTack[™] Motorized Fixation Device, a ventral hernia repair procedure involving a tacker involves risk. These complications are associated with both the procedure itself as well as the devices being used. For patients who are candidates for the study, the benefits of using the MaxTack[™] Motorized Fixation Device during their hernia repair procedure may outweigh these risks.

In conclusion, the MaxTack[™] Motorized Fixation Device has been shown to have a favorable benefit-risk profile based on the criteria of the target population and the risks and benefits potentials of the device.

12. Adverse Events and Device Deficiencies

For enrolled subjects, adverse events (AE) and device deficiencies (DD) will be collected from the time of skin incision until the subject exits. If an AE is considered unresolvable by the investigator, it will be documented within the eCRF that the AE remains unresolved or unrecovered at the time of study exit. Initial reporting of AEs or DDs may be done by phone, email, or by completing as much information as possible on the appropriate eCRF. The completed AE or DD eCRF must be submitted to Medtronic as soon as possible.

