All participating sites will make study data available to the regulatory body if the regulatory body deems an onsite inspection necessary. The regulatory body will be able to inspect records at clinical study sites to resolve any uncertainties about whether the study was conducted in accordance with good clinical practice.

The study will be publicly registered prior to in accordance with the 2007 Food and Drug Administration Amendments ACT (FDAAA) and DoH on http://clinicaltrials.gov (PL 110-85, Section 810(a)).

Approval of the CIP and CIP amendments is required from the following groups prior to any study procedures / revised study procedures at a study site:

- Medtronic
- IRB/EC

This study contains the following from ISO 14155:2020:

AFFIX (MaxTac Clinical Investig				
MDT23014	Revision	3.0	Page 63 of 97	Medtronic

- Point of Enrollment: Per ISO 14155:2020, the point of enrollment is the time at which, following recruitment and before any clinical investigation-related procedures are undertaken, a subject signs and dates the informed consent form. In this study, a subject is considered enrolled when it is confirmed: the ICF is obtained, they meet all preoperative inclusion criteria, and they do not meet any preoperative or intraoperative exclusion criteria, and at least one MaxTack[™] tack is used. (See Section 10.6 for Enrollment details). Those subjects who sign the ICF but fail all screening criteria, will not be included in the study. Those subjects who sign the ICF and are considered intraoperative screen failures will not count as an enrollment.
- Adverse Event Collection: Per ISO 14155:2020, all AEs shall be documented. In this study, only AEs related to the MaxTack[™] motorized fixation device, mesh, or study procedure, all events that lead to death, and any non-subject adverse event will be collected. Additionally, adverse events will be collected starting at the time of skin incision. Enrolled subjects will have adverse events collected from skin incision through study exit.
- Unanticipated Serious Adverse Device Effect (USADE): Per ISO 14155:2020, USADEs are defined as, a SADE, which by its nature, incidence, severity, or outcome has not been identified in the current risk assessment. Due to this being a post-market study, USADEs are not applicable, therefore classification of AEs as such is not required.

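### A MaxTack that fails before its first tack can make the subject an intraoperative screen failure, whose device deficiencies are not reported, so the same-day deficiency endpoint cannot count that failure

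*Protocol*

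**What the plan says.** **Who becomes an intraoperative screen failure.** Section 9.3, intraoperative criterion 1, excludes a subject who did not receive the "Motorized Fixation Device tacks to fixate the mesh". Criterion 9 excludes a subject whose "minimally invasive procedure required to convert to open", whatever the cause. Sections 6 and 15.1 require at least one MaxTack tack for enrolment.

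**What is reported for them.** Section 10.14.2: "Subjects who are considered screen failed during surgery will not have AEs and DDs reported". Section 10.7 says the same for AEs: "the patient will be considered an intraoperative screen failure, and no AEs will be reported". Table 7 requires no AE reporting for this group. The opening of Section 12 sets the scope for both kinds of event: "For enrolled subjects, adverse events (AE) and device deficiencies (DD) will be collected from the time of skin incision until the subject exits". Section 10.14.2 asks only for limited data, with examples ("consent information, reason(s) for not meeting eligibility etc").

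**Where they are analysed.** Section 9.4 introduces Table 2 with "The table below defines the enrollment types that may occur in the study and where these subjects may be analyzed". The entry for intraoperative screen failures is none. Section 15.1 adds: "Those subjects who sign the ICF and are considered intraoperative screen failures will not count as an enrollment". Section 14.5 bases secondary endpoint summaries on the FAS.

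**The endpoint at issue.** Section 5.2.2 lists the incidence of MaxTack deficiencies on the day of the index procedure, with a tacker battery problem among its examples.

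**The concern.** The rule selects on the outcome that the endpoint measures. Under Section 7.1, tack deployment depends on the motor and its circuit board, so a fault at the first firing can mean that no tack is placed. If the surgeon then fixates the mesh by other means, criterion 1 is met and the deficiency goes unreported as a study deficiency. The most complete form of device failure is thus one that the endpoint cannot count.

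Such events are plausible in this study. Table 5 counts use errors as deficiencies, and Section 7.6 allows device training to take place during the physician's first case.

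At stake is a published or regulatory statement of the deficiency rate, together with the intraoperative AEs of the same subjects. Section 4.2 says that the data may be used for both purposes. A reader would take the rate to cover every procedure in which the device was tried, which it does not.

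**Working it through.** The plan states no figure to reproduce. The check is a trace of cases through the rules, followed by an illustration with assumed counts.

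**Trace**

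| Case | Status | Deficiency in the endpoint? |
|---|---|---|
| MaxTack fails before the first tack; MaxTack fixation given up | Criterion 1, screen failure | No |
| MaxTack deficiency, then conversion to open or another intraoperative exclusion | Screen failure | No |
| First MaxTack fails, second MaxTack fixates the mesh, no other exclusion | Enrolled | Yes, from skin incision |
| At least one tack placed, deficiency during use, no other exclusion | Enrolled | Yes |

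For the first two rows, three other records exist:

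- Ineligibility reason (10.14.2): it is recorded, but a criterion 1 entry need not separate device fault from surgeon choice.
- Product complaints (12.6): these go through the regular channels for marketed products.
- Accountability log (7.7): it is updated when a device is opened and its list of contents is open-ended. The subject identifier that it names is that of the implanted subject, so a link to a no-tack subject is not guaranteed.

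None of the three feeds the endpoint.

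**Direction**

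Let d be the deficiencies among the 110 planned enrolled subjects. Let m be the screen failures in whom a MaxTack was opened or attempted, and k those of the m with a deficiency.

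- Reported rate: d/110.
- Device-attempted rate: (d + k)/(110 + m).
- The second exceeds the first when 110(d + k) > d(110 + m), that is 110k > dm, or k/m > d/110.

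The device-attempted rate is therefore higher only if deficiencies are more frequent among the added subjects than in the FAS.

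**Illustration**

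Only the 110 comes from the protocol; d, k and m are assumed. Intervals are 95% Clopper-Pearson.

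| d | k of m | Reported | Device-attempted |
|---|---|---|---|
| 0 | 1 of 5 | 0/110 = 0% (0 to 3.30) | 1/115 = 0.87% (0.02 to 4.75) |
| 0 | 3 of 10 | 0/110 = 0% (0 to 3.30) | 3/120 = 2.50% (0.52 to 7.13) |
| 4 | 0 of 5 | 4/110 = 3.64% (1.00 to 9.05) | 4/115 = 3.48% (0.96 to 8.67) |

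The first two rows rise and the third falls, as the inequality predicts. The table shows how the rule acts and is not an estimate of its effect.

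**The case against.** The strongest defence is that this is a consistent and partly disclosed design choice. The secondary objective concerns the device when used for fixation, and the same boundary appears in Tables 2 and 7 and in Sections 10.6.1, 10.14.2, 12 and 15.1. The device is already cleared, the endpoint is descriptive with no test or threshold, and Section 12.6 requires complaints to be reported at once. Most of this stands, and it limits the weight of the point. It does not remove it: the deficiency endpoint in Section 5.2.2 carries no restriction to completed fixation, and Section 15.1 discloses the enrolment and AE limits but is silent on deficiencies.

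A reader might infer more than the text supports:

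- *That the reported rate is biased in the device's favour by a known amount.* Leaving out a subject with a deficiency does lower the count. The net effect of leaving out the whole group can go either way, and no rate is given from which to size it.
- *That the sponsor would not learn of these failures.* Complaints, the ineligibility reason and the log preserve awareness. What is lost is tabulation in the study.
- *That the log cannot link an opened device to a no-tack subject, or that no deficiency form exists.* The log's list is open, and a deficiency eCRF does exist. The protocol guarantees no such link and does not call for the form in these subjects.
- *That Section 12.7 on deaths after skin incision contradicts Table 7.* It may be meant for enrolled subjects only. That is a separate matter of wording.

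**Conclusion.** The gap holds on the text. A MaxTack deficiency is excluded from the same-day endpoint in two situations: when no tack is placed and MaxTack fixation is given up, and when another intraoperative exclusion then applies. AEs in those subjects are also unreported. No other section brings these events back into the analysis.

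The size cannot be stated, because it depends on device-failure and screen-failure counts that the protocol does not give. Confidence is high that the gap exists, but its practical effect is unknown. The primary recurrence test and the SSO and SSOPI endpoints need no change. The point should be fixed because the rule drops subjects according to the event being measured and the repair is cheap. A SAP could tabulate screen failures by recorded reason, but it could not analyse deficiencies that the protocol says are not reported.

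**What to change.** **Collection.** Amend Sections 10.7, 10.14.2, the opening of 12, 12.4 and Table 7. Record index-procedure deficiencies, and AEs related to device, mesh or procedure up to discharge, on the existing eCRFs for every consented subject in whom a MaxTack was opened or attempted. Discharge is a natural limit because Section 10.14.2 requires no later visits for these subjects. Specify a subject-identifier field for opened or attempted devices in the accountability log or the screen-failure eCRF.

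**Analysis.** Amend Table 2 and Sections 14.2 and 14.5 to define a device-attempted set used only for the deficiency endpoint, and report it beside the FAS result. Without these three changes the new data would conflict with the analysis rules. List screen-failure AEs separately. Show intraoperative screen failures by reason in the CONSORT diagram already planned in Section 14.1.

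**Disclosure.** State the scope of deficiency reporting in Section 15.1.

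Leave the recurrence FAS and the SSO and SSOPI endpoints as they are.

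**Cost.** A few extra forms, one data field, one extra denominator on a descriptive endpoint and a wording amendment. The reported deficiency rate may become less favourable.

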10.14.3 Enrolled Subjects who Complete the Study

At the completion of the Month 12 follow-up visit, subjects will be exited from the study. The Month 12 follow-up visit, and study exit should be combined, and both Month 12 follow-up eCRF and a study exit eCRF need to be completed.

AFFIX (MaxTac Clinical Investig				
MDT23014	Revision	3.0	Page 46 of 97	Medtronic

10.14.4 Withdrawal

A subject can withdraw from the study at any time. If the subject wishes to withdraw from the study (i.e., the subject revokes consent), the study site is required to document the reason for exit and the date on the Exit eCRF. In addition, study sites shall follow the regulations set forth by the IRB or EC. Before the subject withdraws consent, an option for follow-up, which does not include direct contact with the subject, should be offered. This may include medical record review or follow-up with Primary Care Provider or referring physician.

If the study investigator voluntarily removes a subject from further study participation, supporting documentation must be in place for the rationale and date of removal. No subjects should be withdrawn by investigator(s) unless compelling medical justification is present. It is recommended investigators discuss with the Medtronic study team prior to withdrawing subjects. Non-study/routine follow-up of withdrawn subjects will be determined by the investigator according to the standard of care at the respective site. Withdrawn subjects will not be replaced.

10.14.5 Lost to Follow-up (LTFU)

Subject lost to follow-up (LTFU) should be avoided as much as possible, and investigators are urged to do their best to maintain subject follow-up compliance. The site will make every attempt to contact subjects that are noncompliant with study follow-up visits. A subject is considered to be lost to follow-up if the following attempts to contact the subject are unsuccessful:

- Three (3) phone calls should be made to the subject at various times and at least one day apart.
 Each attempt should be clearly documented in the source documents and the response or lack thereof should be captured.
- If there is no response to the phone calls, then an official, certified letter should be written and sent to the subject. A copy of the letter and return or delivery receipts should be retained in the subject's source document.

In case a subject can no longer be found, the monitor shall check the appropriateness of the site's attempts to contact the subject.

The sponsor must be notified, and the study exit eCRF must be completed. The monitor shall check the appropriateness of the site's attempts to contact the subject.

The subject will not be considered lost to follow-up until the end of the study (Month 12 follow-up visit). When subjects are considered lost to follow-up the investigator will make efforts to confirm the vital status/health status of the subject, as described in the informed consent. Lost to Follow-up subjects will not be replaced. At the end of the study, the study exit eCRF will be completed with a status of Lost to Follow-up.

AFFIX (MaxTack [™] Motorized Fixation Device) Clinical Investigation Plan				
MDT23014	Revision	3.0	Page 47 of 97	Medtronic

